#### **Ethical Conduct**

This registry will be conducted in compliance with this document, the principles of Good Clinical Practices and other applicable regulatory requirements or standards.

# 1 PROPPER REGISTRY STUDY SYNOPSIS

Sponsor:	Boston Scientific Corporation (BSC)
Protocol Title (BSC Study Number):	Prospective Registry of Outcomes with Penile Prostheses for Erectile Restoration (PROPPER) (ER1005)
Clinical Phase and Regulatory Status	Post-Market Registry
Study Sites:	Up to 16 sites throughout the USA and Canada
Principal Investigators:	[name], FRCSC University of Ottawa Ontario, Ontario, Canada
	[name] University of South Florida, Tampa, FL, USA
	[name] Urology Centers of Alabama, Birmingham, AL, USA
	[name] Regional Urology; Shreveport, LA, USA
	Additional investigators are expected. The names and addresses of all participating Principal Investigators will be maintained in a separate document.
Objectives:	To understand "real-world" outcomes for men implanted with BSC penile prostheses, including the following: • Safety • Durability • Patient satisfaction • Effectiveness/Quality of Life
Study Design:	Prospective, multi-center, post-market, observational registry, up to 5 year follow-up
Planned Sample Size:	Approximately 500-1500
Inclusion Criteria:	Men diagnosed with erectile dysfunction (ED) for whom a BSC penile prosthesis is recommended by their physician are eligible for inclusion. Potentially eligible men should also meet the following inclusion criteria for study enrollment:
	
 
Willing and able to provide written informed consent prior to enrollment (if applicable).
 

	
 
Willing to be seen or contacted by phone by the investigator and answer at least 2 questions related to treatment satisfaction and device use 1 year following implantation of an BSC penile prosthesis
 

Exclusion Criteria:	Men who are deemed by their physician to be not suitable for a penile implant are excluded from eligibility.
Device Description(s):	
 
Men to be enrolled and followed in this study include those implanted with one of the following marketed BSC penile prostheses:
 
3-piece inflatable penile prosthesis (e.g., AMS 700®)
 
2-piece inflatable penile prosthesis (e.g., AMS Ambicor®)
 
Malleable or concealable penile prosthesis (e.g., Spectra™)
 

Implantation Description:	BSC recommends that all devices are implanted according to the device specific Instruction for Use (IFU) and/or Operating Room (OR) manual and the site or investigator's standard of care.
Concomitant Surgical Procedures:	Concomitant urological procedures are allowed and will be captured; however, outcomes data on these procedures will not be collected, unless an AMS 800 artificial urinary sphincter or AdVance male sling is implanted concomitantly with the BSC penile prostheses. Optional questionnaires will be available to use for assessment.
Implantation Success Measures:	Success will be measured post-operatively by querying patients about treatment satisfaction and device use. Any reported intra-operative and post-treatment complications will be collected in the registry database.
Event Schedule:	Patient data will be collected from the baseline/pre-operative visit, the implantation procedure, and follow-up evaluations which will occur according to each physician's standard of care, up to 5 years post-implantation. A 1-year follow-up evaluation will be required, and a 2-year follow-up evaluation will be strongly encouraged.
Duration of Study:	1-2 year enrollment period Up to 5 year patient follow-up
Measurements:	The registry database will include required measures for all participating investigators to complete and optional

*measures* (listed below in italics) for investigators to complete if they coincide with their standard of care.

Each investigator will be asked basic practice information including:

- Practice type (private, academic)
- Main setting for procedures (Hospital or ASC)
- Do you provide standard device cycling instructions to patients receiving IPPs? If yes, please describe your protocol

Data for each patient for whom a BSC penile implant is recommended will be entered into the registry database at baseline/procedure and at post-implant follow-ups to occur at a minimum 1 year after implantation, and through up to 5 years after implantation.

The baseline/pre-operative data will include:

- Age
- Race/Ethnicity
- Primary etiology of ED
  - o Organic
    - Diabetes
    - Cardiovascular disease
    - Neurologic disorder
    - Peyronie's disease
    - Other organic (specify)
  - o Acute
    - Radical prostatectomy (RP) (robotic, open or laparoscopic)
    - Radical pelvic surgery (other than RP)
    - Pelvic radiation therapy
    - Pelvic trauma or injury
    - Spinal cord injury
    - Venous Leak
    - Priapism
    - Other acute (specify)
- Relevant concomitant medical conditions and concomitant medications that might impact ED (premature or rapid ejaculation/PE, climacturia, cardiovascular disease, diabetes, Peyronie's disease, stress urinary incontinence/SUI, steroid use, anticoagulant use, anti-depressant use, venous leak, and Other, please specify) – with the following sub-

assessments if SUI checked:

- Etiology of incontinence (radical prostatectomy, pelvic irradiation, and other – please specify)
- Previous treatment(s) for incontinence (behavior modification, pelvic floor muscle training, transobturator male sling - specify model and implant date, artificial urinary sphincter/AUS – specify implant model date, other - specify)
- Number of pads used daily
- Pad weight (24-hour test)
- Urodynamics: Post-void residual (PVR) volume (ml), maximum flow rate (ml/sec), any detrusor overactivity (DO) or detruser sphincter dyssynergia (DSD)
- Cystoscopy findings (bladder neck contracture, other – specify)
- Pre-op flaccid penile length (measured from suprapubic fat pad to tip)
- Pre-op stretched penile length (measure from suprapubic fat pad to tip)
- Pre-op flaccid girth (circumference measured 1cm proximal to the proximal end of the corona)
- Duration of ED (years or months)
- Previous ED Treatments [ PDE-5 inhibitors (PDE-5s), vacuum erection device (VED), intracavernosal injection (ICI), Combination therapies, previous/failed penile implants), other, specify]
- Patient query any office visits in past year for treatment of depression Y/N
  - If Yes: approximately how many visits
  - If Yes: taking any depression medication
- Was VED and/or penile traction therapy prescribed pre-operatively? (Y/N)
  - If Yes: specify Duration (weeks) and Frequency (times/day)
- Baseline effectiveness/quality of life assessments

Implantation surgery data will include:

- Date of procedure
- Original (virgin), revision, salvage or replacement implant
  - If revision or salvage, washout (Y/N)

- Surgical approach (Penoscrotal (PS), Infrapubic (IP), Subcoronal (SC) or "Other, please specify")
- Implant model type:
  - Spectra™ Concealable Penile Prosthesis
    - Cylinder diameter (9.5, 12, 14 mm)
    - Cylinder length (12, 16, 20 cm)
    - Total number of RTEs per cylinder (0, 1, 2)
    - Total length of RTEs per cylinder (specify: 0.5 to 7.5 cm)
  - AMS Ambicor® Penile Prosthesis (2-piece inflatable)
    - Cylinder diameter (12.5, 14, 15.5 mm)
    - Cylinder length (14, 16, 18, 20, 22 cm)
    - Total number of RTEs per cylinder (0, 1, 2, 3, 4)
    - Total length of RTEs per cylinder (specify: 0.5 to 6.5 cm)
  - AMS 700® Penile Prosthesis (3–piece inflatable)
    - InhibiZone®-impregnated (Y/N)
    - Cylinder type (CX, LGX, CXR, Ultrex, CXM)
    - Cylinder length (10, 12, 14, 15, 16, 18, 21, 24 cm)
    - Total number of RTEs per cylinder (0, 1, 2, 3, 4)
    - Total length of RTEs per cylinder (specify: 0.5 to 7.5 cm)
    - Pump type (MS Pump, Tactile pump, Inflate/Deflate)
    - Preconnect (Y/N)
    - Reservoir (Spherical 65 ml, Spherical 100 ml, Conceal 100 ml)
    - Reservoir placement (space of Retzius, Sub-muscular, Sub-Scarpa's fascia, other – specify)
    - Reservoir separate incision (Y/N)
- Drain (Y/N)
  - o If Yes, Type
- Dressing
  - None, compression/mummy wrap, noncompressive dressing
- Concurrent procedures (Y/N)
  - If Yes, specify procedure(s): ventral

phalloplasty, ligament release, circumcision, suprapubic fat pad reduction, spermatic cord/testicular procedure, AMS 800 (single or multiple incision), sling (specify sling type and single or multiple incision), other - specify

- Significant corporal fibrosis or scarring noted (Y/N)
- Curvature correction procedure(s) (e.g., for Peyronie's Disease)(Y/N)
  - If Yes: Initial intraoperative curvature measurement (angle of curvature with inflated device using a goniometer or protractor)
  - If Yes: Correction technique (Wilson/Delk remodeling, tunical incision, incision and grafting, or plication)
  - Curvature measurement after correction
  - Second correction? If Yes, same set of questions as above.
- Patient status post-op: Admitted/inpatient/≥24 hours or same day discharge/outpatient/<24 hours
  - If admitted/inpatient/≥24 hours is chosen, include: number of days in the hospital
- Length of procedure (measured from time of first incision to time of closure)
- Intra-operative penile length measurement with device inflated (measured from suprapubic fat pad to tip)
- Intra-op penile girth measurement with device inflated (circumference measured 1cm proximal to the proximal end of the corona)
- Intra-op stretched penile length measurement with device deflated (measured from suprapubic fat pad to tip)
- Foley in place at discharge? (Y/N)

Follow-up is required 1 year post-operatively. *Additional follow-ups will be determined per the physician's standard practice up to 5 years.* Follow-up data will include:

- Query for any device related complications and their outcomes by asking patients if they have had any surgery on their penis or problems with the device since their penile prosthesis was implanted (Y/N)
- Patients will be asked:
  - How satisfied they are with the device(s) (using a 5-point scale)

- If they are using the device (Y/N)
  - If yes, how often they are using the device (less than once per month or more than once per month)
     *o* How many times per month?
  - If no, why aren't you using the device (loss of partner, partner disinterest, device problem, device dissatisfaction, health decline, other – describe, other device use reason).
  - If yes, and not using the device as often as desired, or if dissatisfied with the device, indicate why ((loss of partner, partner disinterest, device problem, device dissatisfaction, health decline, other – describe, other device use reason).
- Number of pads used daily (if incontinence indicated pre-operatively)
- Pad weight (24-hour test) (if incontinence indicated pre-operatively)
- Penile length measurement with device fully inflated (measured from suprapubic fat pad to tip)
- Penile girth measurement with device fully inflated (circumference measured 1cm proximal to the proximal end of the corona)
- Stretched penile length measurement with device deflated (measured from suprapubic fat pad to tip)
- Patient query any office visits in past year for treatment of depression Y/N
  - o If Yes: approximately how many visits
  - If Yes: taking any depression medication
- Effectiveness/quality of life assessments

Patient questionnaires to measure effectiveness will be optional at baseline and at all follow-up visits. Included are the following validated, patient-reported outcome questionnaires:

#### Strongly recommended for all:

- IIEF-5/SHIM erectile function questionnaire
- EHS erection hardness questionnaire
- SF-12 health-related quality of life questionnaire

Effectiveness Assessments:

#### *Recommended for all patients with post-prostatectomy ED or incontinence:*

- AUA-SI/IPSS urinary symptom questionnaire
- UCLA-PCI urinary, sexual and bowel function and bother questionnaire

Any reported intra-operative or post-operative device or surgery related complications will be recorded throughout study follow-up (for BSC products only). This information will include:

- Complication
- Treatment
- Location of treatment

• Resolution (Resolved or Continuing) Potential device or surgery related complications are described in the device specific IFU and OR manuals.

Up to 1500 patients with erectile dysfunction (ED) electing to receive a BSC penile prosthesis implant will be included in this registry.

Analyses of multi-center data for initial publication(s) may be performed after approximately 500 patients complete 1 year follow-up. Additional individual and multi-center data analyses may be performed as warranted throughout the study for publication(s). Analysis for multi-center publication(s) is planned after the study enrollment is complete and all the enrolled patients have completed their one-year and five-year follow-up evaluations, consistent with each physician's standard of care.

Continuous variables will be presented as mean +/- SD; ordinal variables will be summarized using median with interquartile ranges; categorical variables will be presented as count and proportion.

Kaplan-Meier method will be used to estimate the event rate over time by device type for major complications.

For within-patient change at 1 year follow up compared to the baseline visit, signed rank test or paired t-test may be used for continuous variables and McNemar's test may be used for binary variables when applicable. Mixed effects model or Generalized Estimating Equation model may be used to estimate the change from baseline across follow up

Safety/Device Malfunction Assessments:

Statistical Analyses, Including Determination of Sample Size: visits when appropriate.

The data to be collected in electronic data forms will include the following:

Table 1: Electronic	; data	collection	schedule
---------------------	--------	------------	----------

Data	Baseline/ Procedure	Interim Follow-Up*	1 Year Follow-Up*	2 - 5 Year (Annual) Follow-Up*
Date of Informed Consent/first data record	R			
Demographics and Characteristics	R			
ED History	R			
Depression History	0	N/A	0	0
Implantation Procedure Details	R			
Device Use and Satisfaction	N/A	0	R	SE
Penile Measurements	0	0	0	0
Incontinence Data	0	0	0	0
Patient Questionnaires	SE	SE	SE	SE
Clinical Study Events/Complications	R†	R†	R†	R†

\* The same assessments, evaluations, questionnaires that were completed at baseline should be completed at follow-up

[figure not shown]
R = Required, O = Optional, SE = Strongly Encouraged, N/A = Not Applicable.

 $\dagger = if applicable$ 

- Demographics and Characteristics age, race/ethnicity, concomitant medical conditions and medications
- ED History primary etiology of ED, previous ED treatments (optional)
- Depression History query for any treatment of depression in past year optional at baseline and at annual follow-up
- Implantation Procedure Details surgical procedure details and implant model information, patient status post-op
- Device Use and Satisfaction query for device use and device satisfaction
- Penile Measurements pre-op flaccid and stretched length and girth, intra-op inflated penile length and girth and deflated stretched length, and post-operative inflated length and girth measurements, by physician
- Incontinence Data Daily pad use, pad weight tests, urodynamics, post-void residual (PVR) volume maximum flow rate

- Patient Questionnaires IIEF-5/SHIM erectile function questionnaire; EHS erection hardness question; SF-12 health-related quality of life questionnaire; AUA-SI symptom questionnaire; UCLA-PCI urinary, sexual and bowel function and bother questionnaire
- Clinical study events device or procedure related complications (adverse device effects/events), device malfunctions, revision procedures related to the device or implantation procedure

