# 7.4.1 CLINICAL STUDY EVENTS

Clinical study events to be collected for assessment of safety include complications (adverse device effects/events), device malfunctions, and revision procedures related to the device or implantation procedure. At follow-up, including the required 1-year post-operative visit or telephone call, the following standardized, non-validated question will be used to determine whether any complications with the device have occurred:

• Have you had any surgery on your penis or problems with the device since your penile prosthesis was implanted? (Y/N)

A clinical study event data form will be provided to record any events that occur during or after surgical implantation of a BSC penile prosthesis device. Any reported intraoperative or post-operative device or surgery related complications should be recorded at the time of procedure and any follow-up visits (for BSC products only). The information recorded will include the following:

- Complication
- Treatment
- Location of treatment
- Resolution (Resolved or Continuing)

BSC personnel will follow up with the physician to obtain additional available details, if needed, related to any reported complication that results in a serious adverse device effect, or device deficiency that could have led to a serious adverse device effect, or is severe and may pose unreasonable risk, or potential for death, or serious injury to the patient.

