# 8 STATISTICAL METHODS AND DATA ANALYSIS

Analyses of multi-center data for initial publication(s) may be performed after approximately 500 patients complete 1 year follow-up. Additional individual and multicenter data analyses may be performed as warranted throughout the study for publication(s). Analysis for study publications is planned after the study enrollment is complete and all the enrolled patients have completed their 1-year and 5-year follow-up evaluations.

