#### Endpoint:

- Complications (adverse device effects/events)
  - Intra-operative device or surgery related complications reported during Implantation visit (e.g., cylinder crossover)

- Post-operative device or surgery related complications reported during follow-up (e.g., mechanical malfunction, infection)
- Unanticipated and serious adverse device effects (per ISO 14155:2011)
- Deaths (related to the device or implantation procedure)
- Device Malfunctions
  - Device deficiencies or malfunctions (per ISO 14155:2011)
- Revision procedures related to the device or implantation procedure

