#### Statistical Analysis:

Descriptive statistics (number of events, number and proportion of patients) will be summarized by complication category by device type and for the full group. Kaplan-Meier method will be used to estimate the major complication event rate at 1 year postoperative follow up by device type and overall for all BSC penile prostheses recipients.

Descriptions will also be prepared of the following details associated with device related complications in each category, and will include the following as available for each:

- Treatment for complication
- Location of treatment
- Resolution (resolved or continuing)

Additional analyses may be prepared for other follow-up time such as 6 month, 2, 3, 4, and 5 years.

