## 16.1 PHYSICIAN REPORTS

Physician is responsible for preparation and submission of the following reports as identified in Table 5 below.

Report	Submit to	Description
Clinical Study Events	Sponsor/IRB/EC	Unanticipated adverse device Effect (UADE), and Serious Adverse Device Effect (SADE) need to be submitted to the Sponsor and may need to be submitted to the IRB/EC in accordance with the IRB/EC requirements at the study site, as soon as possible but no later than 10 working days after the physician learns of the event
Study Patient Death	Sponsor/IRB/EC	Death must be reported to the sponsor and may need to be submitted to the IRB/EC in accordance with local requirements, no later than 10 working days after the physician learns of the death
Withdrawal of IRB/EC approval	Sponsor	The physician must report a withdrawal of approval by the reviewing EC/ IRB of the physician's part of the study, within 5 working days of the physician learning of the withdrawal of approval
Progress Report	Sponsor/IRB/EC	The physician must submit this report to the sponsor and the IRB/EC at regular intervals in accordance with the IRB/ EC requirements at

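### Beyond 1 year, Kaplan-Meier with unrelated deaths censored by default would estimate a net risk and modestly overstate the share of implanted men who have a major complication

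*Combined protocol and SAP*

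**What the plan says.** **Estimator.** The synopsis (Statistical Analyses) says: "Kaplan-Meier method will be used to estimate the event rate over time by device type for major complications". It gives no time limit. Section 8.2 (Statistical Analysis) is narrower: "Kaplan-Meier method will be used to estimate the major complication event rate at 1 year postoperative follow up by device type", and also overall. It then adds: "Additional analyses may be prepared for other follow-up time such as 6 month, 2, 3, 4, and 5 years". So 1 year is firm and the later years are optional.

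**Horizon.** The synopsis describes the duration as "1-2 year enrollment period Up to 5 year patient follow-up". Section 8 plans a publication analysis once "all the enrolled patients have completed their 1-year and 5-year follow-up evaluations".

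**Deaths.** The section 8.2 endpoint list includes "Deaths (related to the device or implantation procedure" and no other deaths. Section 7.4.1 limits the safety events collected to "complications (adverse device effects/events), device malfunctions, and revision procedures related to the device or implantation procedure". Reporting is wider. Under Study Patient Death, Table 5 in section 16.1 says: "Death must be reported to the sponsor and may need to be submitted to the IRB/EC in accordance with local requirements". It sets no relatedness condition.

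**Not stated.** No section gives a censoring rule, says how an unrelated death enters the Kaplan-Meier estimate, or names a competing-risk method. Neither the synopsis nor section 8.2 says which complications count as major.

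**The concern.** A man who dies of something else can no longer have a device complication. If his time is censored at death, Kaplan-Meier treats him as still able to have one later, like the men who remain under observation. One minus Kaplan-Meier is then a net risk: what would be seen if unrelated death did not occur. It is at least as large as the proportion of implanted men who actually have a major complication, and strictly larger once unrelated deaths occur before later complications.

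This matters because section 3.1 aims to describe real-world outcomes, with safety and durability both listed. The two call for different quantities: the share of men affected for safety, and the net risk for durability. The plan calls its estimate an event rate without saying which is meant. Competing death is foreseeable here. Section 2.1 links erectile dysfunction to raised mortality through cardiovascular disease, and section 8.4.1 names diabetes, cardiovascular disease and radical prostatectomy among its etiology subgroups.

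**Working it through.** The plan states no complication, mortality or loss rate, so there is no figure to reproduce. Every rate below is an assumption. The group sizes come from section 8.1.

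**Model.** Constant, independent hazards *a* (complication) and *d* (unrelated death) over *T* years, each obtained as −ln(1 − risk)/T.

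- Death censored: 1 − KM = 1 − exp(−aT)
- Death as competing event: CIF = a/(a+d) × [1 − exp(−(a+d)T)]
- Greenwood standard error (SE), with loss hazard *l* and k = a+d+l: (1 − R) × √{(a/(nk)) × [exp(kT) − 1]}, where R is the net complication risk

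**1 year.** With complication 5-8% and death 1-3%, the difference is 0.02 to 0.12 points.

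**5 years, central case (complication 15%, death 10%).**

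- a = −ln(0.85)/5 = 0.03250; d = −ln(0.90)/5 = 0.02107
- CIF = 0.03250/0.05358 × (1 − 0.85 × 0.90) = 0.6067 × 0.235 = 14.26%
- Excess = 15.00 − 14.26 = 0.74 points
- With n = 1000 and half lost by year 5, l = −ln(0.5)/5 = 0.13863 and k = 0.19221. SE = 0.85 × √{0.03250/(1000 × 0.19221) × 1.614} = 1.40 points, so the excess is 0.74/1.40 = 0.53 SE.

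**5 years, range, n = 1000 with 50% loss.** The right-hand columns put half of the 5-year cumulative complication hazard in year 1.

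| Complication | Death | Excess, constant hazard (points) | In SE | Excess, early clustering (points) | In SE |
|---|---|---|---|---|---|
| 10% | 5% | 0.25 | 0.21 | 0.17 | 0.16 |
| 10% | 15% | 0.76 | 0.63 | 0.53 | 0.47 |
| 15% | 10% | 0.74 | 0.53 | 0.52 | 0.39 |
| 25% | 5% | 0.60 | 0.36 | 0.41 | 0.26 |
| 25% | 15% | 1.84 | 1.06 | 1.26 | 0.77 |

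Over the grid of complication 10, 15, 20, 25% by death 5, 10, 15%, the constant-hazard excess is 0.25 to 1.84 points. At n = 1000 with 50% loss, one of the 12 cells exceeds 1 SE. At n = 1500 with 50% loss, two do, the larger at 1.29 SE.

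**A second set of assumptions.** With net 5-year risk 5-20% and annual mortality 1-5%, the 5-year excess is 0.12 to 2.27 points and the 1-year excess 0.01 to 0.11 points. The upper end implies 5-year mortality of 1 − 0.95⁵ = 22.6%, beyond the range in the table.

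**By device.** Section 8.1 projects 500 AMS 700, 15 Ambicor and 20 Spectra implants per year. One to two years of enrollment gives 500-1000, 15-30 and 20-40. In the central case with 50% loss, the SE is 11.5 points at n = 15 and 7.0 points at n = 40. The 0.74-point excess is then 0.06 to 0.11 SE.

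**The case against.** **No commitment to 5-year curves.** A reader might infer that the plan commits to 5-year Kaplan-Meier estimates. It does not. The only firm time point is 1 year, where the effect is negligible. This stands. What remains is that the synopsis sets no limit and a 5-year analysis is planned, so later curves are likely.

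**Censoring is an inference.** A reader might infer that the plan prescribes censoring at death. No section says so. Death could be made part of the event, or men who die could be kept in the risk set to their administrative end date. Censoring is only the default when Kaplan-Meier is the sole named estimator and unrelated death is outside the endpoint. The documented gap is an unstated rule.

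**The net curve is legitimate.** Durability is a separate objective, and a death-censored curve answers it. This also stands. The curve overstates risk only when read as the share of men affected, and the plan does not say how it is to be read.

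**Death data may be incomplete.** Table 1 has no vital-status item. The 2-year visit is only encouraged, later follow-up depends on each physician's practice, and the Table 5 clock starts when the physician learns of the death. Late deaths may look like loss to follow-up, and Aalen-Johansen would censor those too. A reader might infer that required death reports allow a full correction; the documents support only a partial one.

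**Size is assumed.** One might claim that 15% mortality always moves the estimate by more than half a standard error at n = 1000. It does not: with 10% complication and early clustering it is 0.47 SE. In the central case, 70% or 80% loss lowers the ratio from 0.53 to 0.45 or 0.40 SE.

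**Total mortality.** One might infer that it will never be tabulated. The plan lists only related deaths but nowhere excludes an all-cause table.

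**Conclusion.** The point holds as a small improvement to the plan. The documents do not support the statement that the registry's long-term complication risk is overstated. They support a conditional one: if Kaplan-Meier is used beyond 1 year, unrelated deaths are censored as the default implies, and the result is read as the share of implanted men with a major complication, it is biased upward.

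The 1-year estimate can stand. At 5 years the excess is about 0.2 to 1.8 points under the assumed rates (complication 10-25%, unrelated death 5-15%, constant independent hazards). It falls by roughly 30% if half of the complication hazard lies in year 1. It is usually below one standard error for AMS 700 or the pooled group, and lost in sampling error for Ambicor and Spectra. The direction is secure; the size rests wholly on rates the documents do not give.

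**What to change.** In section 8.2 and in the synopsis:

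1. State how unrelated death is handled in the analysis of major complications.
2. For any estimate beyond 1 year, report the Aalen-Johansen cumulative incidence with unrelated death as the competing event.
3. Keep Kaplan-Meier as a second curve, labelled net device durability.
4. Tabulate all deaths reported under Table 5, split into related and unrelated.
5. Note in the report that vital status is not a scheduled item, so unreported late deaths remain censored and the correction is partial.

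**Cost.** A few sentences of plan text, one further estimate from standard software and one table. No change to the design, sample size or visit schedule is needed. The downside is two curves to explain instead of one. Capturing late deaths fully would need a vital-status item in data collection, which is a larger change and is not required for this fix.
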